6.4.2 Secondary Efficacy Endpoints

Not applicable.

6.5 SAFETY ANALYSES

The safety analysis population will include all participants in the safety population who received at least one dose of study drug. The following safety outcome measures will be summarized using descriptive statistics:

- Incidence, nature, severity, and timing of adverse events
- Incidence, nature, severity, and timing of serious adverse events
- Changes from baseline of this study in vital signs, blood tests, ECGs, and C-SSRS
- Incidence, nature, severity, and timing of MRI safety findings: ARIA-E and ARIA-H
- Incidence, nature, severity, and timing of ISRs
- Number and proportion of ADA-positive and ADA-negative participants during both the treatment and follow-up periods
- Incidence of treatment discontinuations for adverse events
- Incidence of adverse events of special interest

Statistical methods, endpoint definitions and analyses of the safety endpoints will be described in the Statistical Analysis Plan.

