Participants will be treated for 2 years, followed by a safety and MMSE assessment 4 weeks following the last dose (follow-up visit; see Schedule of Activities).

Participants who discontinue study drug at any time during this study will be asked to complete an early termination visit 4 weeks after their last dose (early termination visit; see [Appendix 1](#)).

3.1.2 Overview of the Study Design in Part 2

All participants who are actively enrolled in Part 1 of Study WN41874 (i.e., have completed Week 104 visit in Part 1 and have not discontinued from study drug per Section 4.6.1) will be invited to participate in Part 2 of the study.

Informed consent should be obtained by participants while they are active in the Part 1 of the study.

In Part 2 of the study, participants who have previously completed the Week 104 visit, (i.e., without having to perform a follow up visit post Week 104 in Part 1) can continue receiving open-label gantenerumab for additional 2 years. Additionally, participants might also have an option of participating in another open label extension study while completing the Part 2 of the study.

Gantenerumab will be administered by SC injection Q4W at the same dose as administered in the Part 1 of the study. There is a ± 7 day window for all visits. However, the minimal time between doses is 21 days, and the target day for each Q4W visit is timed with respect to baseline, not to the prior visit.

Participants will be treated for an additional 2 years, followed by a safety and MMSE assessment 4 weeks following the last dose (follow-up visit; see [Appendix 1](#)).
Participants will undergo tests of safety, efficacy as per the schedule of assessments.

The end of the study will be considered as the follow-up visit 4 weeks after the last dose for the last participant that enrolled over to Part 2.

All participants have the right to voluntarily discontinue study drug or withdraw from the study at any time for any reason.

Participants who discontinue study drug at any time during this study will be asked to complete a follow-up visit at 4 weeks after their last dose (*early termination visit*; see [Appendix 1](#)).

Participants who do not want to participate in Part 2 of the study will be discontinued from the study and will be asked to complete follow up visit 4 weeks after the last dose as per the Schedule of Assessments (follow up visit; see [Appendix 1](#)).

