4.5 STUDY ASSESSMENTS

The study assessments are detailed in the following sections. Please see [Appendix 1](#) for the Schedule of Activities.

At applicable sites, certain study assessments may be performed by a MN professional at the participant's home or nursing center to improve access and convenience for participants participating in the study. *Mobile nursing can be provided for the visits where attendance at the study site is not considered necessary (i.e., at visits except for Week 24, Week 52, Week 76, Week 104, Week 128, Week 156, Week 180, and Week 208).* The Sponsor will select a healthcare company that will be responsible for providing HN services for participating sites (the MN vendor). The MN vendor is responsible for ensuring that all MN professionals are licensed, qualified, and in good standing, per applicable regulations, and that appropriate background checks have been performed. If the investigator at a participating site determines that MN services are appropriate for a participant and the participant gives written informed consent to participate in MN visits, the MN network will communicate with the participant and the participant's site. *Mobile nursing* visits will be scheduled on specified visit days to allow relevant assessments to be performed by the MN professional.

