4.5.8 Columbia-Suicide Severity Rating Scale

The C-SSRS (<http://www.cssrs.columbia.edu>) is an assessment tool used to assess any new instances of suicidality (C-SSRS >6 months since last visit). The structured interview prompts recollection of suicidal ideation, including the intensity of the ideation, behavior, and attempts with actual or potential lethality. The C-SSRS since the last visit will be collected at visits as indicated in the Schedule of Activities (see [Appendix 1](#)). The assessment will be completed by a certified C-SSRS rater after he or she interviews the participant and the participant's caregiver during the study visit.

The baseline (Day 1) C-SSRS for the participants participating in this study will be the same as in the post-treatment follow-up visit in Studies WN25203 and WN28745. If the last C-SSRS assessment was completed more than 6 months from the baseline visit, the assessment has to be repeated, *this* will be recorded in the eCRF *at the baseline (Day 1) visit*.

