Appendix 1 Schedule of Activities (Part 1 and Part 2)

ADA= anti-drug antibody; ALT/SGPT =alanine aminotransferase/serum glutamicpyruvic transaminase; ARIA = amyloid-related imaging abnormality; ARIA-E = amyloid-related imaging abnormality-edema/effusion; ARIA-H = amyloid-related imaging abnormality–hemosiderin deposition; AST/SGOT = aspartate aminotransferase/serum glutamicoxaloacetic transaminase; BP = blood pressure; BUN = blood urea nitrogen; C-SSRS = Columbia-Suicide Severity Rating Scale; ECG = electrocardiogram; F1 = follow-up 1; HR = heart rate; ICF = Informed Consent Form; IMP = investigational medicinal product; MMSE = Mini Mental State Examination; MRI = magnetic resonance imaging; PI = Principal Investigator; PK = pharmacokinetic; Q4W = every 4 weeks; UV = Unscheduled Visit; WBC = white blood cell.

Notes: There is a ± 7 day window for all visits. However, the minimal time between doses is 21 days, and the target day for each Q4W visit is timed with respect to baseline, not to the prior visit.

Participants who will undergo an up-titration step, due to a dose gap of more than 16 weeks (see [Appendix 3](#)), will follow the same Schedule of Activities, except that an additional MRI will be performed before up-titration (further details in [Appendix 3](#)). Also, participants who have their dosing modified due to an ARIA-E event will follow the same Schedule of Activities, with the exception of any additional safety MRI scans that might be required (see [Appendix 2](#)).

- a Day 1 visit is the baseline visit and the visit of the first IMP administration for this study. Day 1 visit should take place on the same day as the follow-up visit (4 weeks after last dose) of the qualifying studies whenever possible.
The Day 1 vital signs, serum chemistry and hematology, urine pregnancy test, and physical examination results will be the same as in the post-treatment follow-up visit in Studies WN25203 and WN28745 if they occur on the same day or within 4 weeks.
The Day 1 MRI, MMSE, and C-SSRS will be the same as in the post-treatment follow-up visit in Studies WN25203 and WN28745 if they occur on the same day or within 6 months.

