Appendix 1 Schedule of Activities (Part 1 and Part 2)

- ^g Serum chemistry includes AST/SGOT, ALT/SGPT, alkaline phosphatase, total protein, total bilirubin, serum albumin, CPK, sodium, potassium, calcium, BUN, and serum creatinine (and creatinine clearance calculated by the central laboratory).
Hematology includes hemoglobin, hematocrit, red blood cell (with morphology), WBCs, platelet, basophil, eosinophil, lymphocyte, monocyte, neutrophil, and WBC–other total counts.
- ^h At all visits where biomarker plasma, PK, and ADA samples are needed, the samples should be obtained before administration of gantenerumab if applicable. Accurate recording of the time of study drug administration and PK sampling is critical.
- ⁱ Female *participants* of childbearing potential (including those who have had a tubal ligation) must have a urine pregnancy test performed at the site prior to each dose administration. If a urine pregnancy test is positive, it must be confirmed by a serum pregnancy test at the central laboratory.
- ^j C-SSRS (since last visit) should be obtained every 6 months *and additionally* at any time deemed necessary by the investigator.
- ^k *Only the relevant assessments will be performed, determined per the investigator’s clinical judgment, and do not necessarily include all those listed above.*
- ^l *MRI must be performed within 20 days after dose administration and results made available and reviewed before the final follow-up or drop-out visit to allow review before the final visit. Participants will be asked if they experience CNS adverse events up to one week before each MRI is performed.*

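### C-SSRS is listed as a change from baseline, although each form records events over a look-back period of unequal length

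*Combined protocol and SAP*

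**What the plan says.** **Analysis.** Section 6.5 lists, among the safety outcomes for descriptive summary, "Changes from baseline of this study in vital signs, blood tests, ECGs, and C-SSRS". The synopsis has the same item. Section 6.5 leaves methods and endpoint definitions to a Statistical Analysis Plan. The documents available contain no further rule for the C-SSRS.

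**Instrument.** Section 4.5.8 describes the scale as a means of detecting new instances of suicidality and states: "The C-SSRS since the last visit will be collected at visits as indicated in the Schedule of Activities". Footnote j of Appendix 1 adds: "C-SSRS (since last visit) should be obtained every 6 months", with further forms whenever the investigator thinks them necessary.

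**Timing.** The Schedule of Activities marks the C-SSRS at Day 1, then at the visits that Section 4.5 also names as requiring site attendance ("Week 24, Week 52, Week 76, Week 104, Week 128, Week 156, Week 180, and Week 208"), at the follow-up or early termination visit, and at unscheduled visits. Under Sections 3.1.1 and 3.1.2, treatment is "followed by a safety and MMSE assessment 4 weeks following the last dose". Dosing visits are every 4 weeks.

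**Baseline.** Footnote a of Appendix 1 says: "The Day 1 MRI, MMSE, and C-SSRS will be the same as in the post-treatment follow-up visit" of the parent studies, "if they occur on the same day or within 6 months". Section 4.5.8 agrees: "If the last C-SSRS assessment was completed more than 6 months from the baseline visit, the assessment has to be repeated". Day 1 is the day of the first dose in this study.

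**The concern.** Blood pressure or a laboratory value is a state at a point in time, so its change from baseline has a plain meaning. A since-last-visit C-SSRS form says whether ideation or behaviour occurred during a period. Comparing two such forms is informative only if the periods are of similar length and fall on the intended side of the first dose.

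Three things follow if the look-back runs from the previous C-SSRS. A short follow-up window will tend to show fewer events than a long on-treatment window, which can look like improvement. A participant with the same finding at Day 1 and on study contributes no change, although an on-study event occurred. Where the Day 1 form is an old parent-study form, events before the first dose can be counted as on-study.

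The plan also does not say which visit is the last one. With 4-weekly dosing visits, a rater could take it to be the previous dosing visit and ask about only the past 4 weeks. The C-SSRS is a listed endpoint of the main safety objective, so both the question asked and the summary should be unambiguous.

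**Working it through.** The plan gives no figure to reproduce. The check is interval arithmetic on the Schedule of Activities.

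**Reading A: look-back runs from the previous C-SSRS.** Look-back = week of the form minus week of the previous form.

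| Form | Look-back (weeks) |
|---|---|
| W24, W76, W128, W180 | 24 |
| W52, W104, W156, W208 | 28 |
| Completer's follow-up (W108 or W212) | 4 |

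The mean on-treatment interval is (4 × 24 + 4 × 28)/8 = 26 weeks, which agrees with the six-monthly frequency in footnote j. Early termination shares a column with follow-up. After Week 24 its look-back can be anything from about 4 to 28 weeks, depending on when treatment stops. The look-back of the Day 1 form belongs to the parent study and is not stated.

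**Carry-over under Reading A.** The W24 form covers gap + 24 weeks, where the gap is the time from the parent-study form to Day 1. Six months is 365.25/2/7 = 26.1 weeks.

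| Gap (weeks) | W24 form covers (weeks) | Share before first dose |
|---|---|---|
| 0 | 24 | 0% |
| 4 | 28 | 4/28 = 14% |
| 16 | 40 | 16/40 = 40% |
| 26.1 (longest permitted) | 50.1 | 26.1/50.1 = 52% |

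**What unequal windows do.** The documents give no event rate, so as an assumption take a constant rate r per person-year. The chance of at least one event in w weeks is 1 − exp(−r × w/52.18).

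| Assumed events per 100 person-years | 4 weeks | 28 weeks |
|---|---|---|
| 2 | 0.15% | 1.07% |
| 5 | 0.38% | 2.65% |
| 10 | 0.76% | 5.22% |

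With no change in risk, the follow-up percentage is about one seventh of that from a 28-week form (4/28 = 14%). In 116 participants, the Part 1 total and so an upper limit, the middle row is 116 × 2.65% ≈ 3.1 against 116 × 0.38% ≈ 0.4 participants with an event.

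**Reading B: look-back runs from the previous 4-weekly visit.** Each scheduled form covers about 4 weeks. The windows are then equal and the W24 form does not reach Day 1, but 24 − 4 = 20 or 28 − 4 = 24 weeks of each interval are not assessed on the scale. For a participant completing Part 1 only, five forms cover 20 of 108 weeks (19%). Over both parts, nine forms cover 36 of 212 weeks (17%).

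**Which reading the text supports.** Section 4.5.8 attaches a period of more than six months to the phrase about the last visit, and footnote j gives a six-monthly frequency. Both fit Reading A, because dosing visits are scheduled 4 weeks apart. Neither passage says so outright, and the example adverse-event questions in Section 5.3.2 refer to the last visit in its ordinary visit-to-visit sense.

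**The case against.** **The method is deferred.** Section 6.5 specifies no arithmetic C-SSRS change score, and a categorical shift table is also a change from baseline. A reader might infer that the plan commits to subtracting scores; the documents do not support that. What stands is that the only measure named is change from baseline, in one line with vital signs, and no C-SSRS rule accompanies it. A later plan could choose a better summary but could not recover what raters did not ask.

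**The long window is an extreme.** Day 1 should coincide with the parent follow-up visit where possible, and the W24 form then has no pre-dose part. A reader might take a range of 4 to 50 weeks as typical; it is not. Long gaps are nevertheless foreseen: Section 3.1.1 mentions approval delays, and Appendix 3 provides for dosing gaps over 16 weeks. Since the parent follow-up is 4 weeks after the last parent dose, such a gap can put more than 16 − 4 = 12 weeks before Day 1 into the W24 window.

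**The two readings cannot be combined.** A reader might add the unassessed weeks of Reading B to the long windows of Reading A. They are alternatives: scheduled coverage is continuous under A, and no scheduled form covers 50 weeks under B.

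**Adverse events are collected anyway.** All adverse events after the first dose are recorded (Section 5.3.1) and their timing is summarised, and extra C-SSRS forms are allowed. It would therefore be too strong to say that new suicidality on treatment cannot be seen. The protection is partial, because Section 5.3.2 asks for non-directive questioning, whereas the C-SSRS interview prompts specifically for ideation, behaviour and attempts.

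**Consequence is limited.** The study is open-label and descriptive, and suicidality is not an identified risk of the drug. This limits the weight of the point but is no reason to keep a summary that is hard to interpret.

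**Conclusion.** The point holds and should be acted on. Under the reading that the text favours, scheduled look-backs of 24 or 28 weeks on treatment and 4 weeks at follow-up mean that a visit-wise change from baseline does not compare like with like. That seven-fold difference arises even when Day 1 coincides with the parent follow-up. Carry-over of the Day 1 form adds a pre-dose part to the W24 form, from none up to about 26 of 50 weeks; the number of participants affected is not given. The undefined last visit is a separate ambiguity that matters most for what raters ask in Part 2.

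This rests on scheduled visits taking place as planned, on six months being about 26 weeks, and on there being no C-SSRS rule in a plan outside the documents available. How much the summary would mislead depends on event rates that the documents do not give.

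**What to change.** 1. In Section 4.5.8 and footnote j of Appendix 1, define the look-back as running since the last C-SSRS assessment. Part 1 forms already completed cannot be changed, but this still protects Part 2.
2. In Section 6.5 and the synopsis, take the C-SSRS out of the change-from-baseline item. Report instead the number and percentage of participants with any suicidal ideation and with any suicidal behaviour after Day 1, separately for Part 1 and Part 2 because follow-up differs. Show the Day 1 category alongside as context, not for subtraction, and identify the follow-up form separately.
3. From assessment dates already held, flag W24 forms whose look-back starts before Day 1, and show the result with and without them. This is preferable to a new onset-date field: all 116 Part 1 participants are enrolled, many W24 forms must already exist, and events would have to be dated retrospectively in people with Alzheimer's disease.

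The cost is wording in three places plus the synopsis and slightly more analysis work. No visits or assessments are added.

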In the double-blind part of Study WN25203, ARIA events were dependent on time (duration of treatment), dose, and APOE ϵ 4 allele status. The frequency of ARIA-E MRI findings was 0.8%, 6.6%, and 13.5% and the frequency of ARIA-H was 13.2%, 22.9%, and 16.2% in the placebo, 105-mg gantenerumab, and 225-mg gantenerumab groups, respectively.

Generally, ARIA events were asymptomatic and resolved spontaneously; discontinuation due to protocol-mandated rules for ARIA-E or ARIA-H occurred in less than 5% of participants.

In the double-blind part of Study WN28745, the frequency of new ARIA-E was 1.5% and 11.5% and the frequency of ARIA-H was 11.8% and 15.1% in the placebo and gantenerumab groups, respectively. Most ARIAs were asymptomatic and did not lead to clinically significant consequences. One participant (0.5%) in the placebo and gantenerumab groups each reported symptoms related to ARIA, which were mild to moderate and non-serious. Discontinuation due to protocol-mandated rules for ARIA-E or ARIA-H occurred in approximately 3.4% of participants.

In the OLE part of Study WN25203, all 154 participants dosed with gantenerumab *in the OLE* had *at least one* post-OLE baseline MRI scan. *Of these*, 47 participants (30.5%) had new ARIA-E and 51 participants (33.1%) had new ARIA-H. *Additionally*, 31 participants (20.1%) had new ARIA-E and new ARIA-H at any point during the OLE. *The CNS adverse events temporally associated ARIA-E MRI findings were mostly non-serious, mild to moderate in intensity, and resolved spontaneously with protocol-defined ARIA management rules. None of these adverse events led to permanent discontinuation of study treatment.*

In OLE part of the Study WN28745 and up to snapshot date of 11 January 2021, 219 of 225 participants dosed with gantenerumab *in the OLE phase* had a post-baseline MRI scan. *Of these*, 71 participants (32.4%) had new ARIA-E and 75 participants (34.24%) had new ARIA-H. *Additionally*, 49 participants (22.37%) had new ARIA-E and ARIA-H at any point during the OLE. The CNS adverse events were mostly mild to moderate in intensity, non-serious, did not require permanent cessation of study treatment, and resolved spontaneously with protocol-defined ARIA management rules. *None of these adverse events led to permanent discontinuation of study treatment.*

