4.1.2 Exclusion Criteria

Participants who met any of the following criteria *will* not be eligible:

- Prematurely discontinued from the OLEs of Studies WN25203 or WN28745 or from study drug for any reason
- Any medical condition that the investigator or Sponsor determines may jeopardize the participant’s safety if he or she continues to receive study treatment
- If the participant is unlikely to benefit from gantenerumab therapy, based on disease progression or other factors, or if study participation is otherwise not in the participant’s best interest, by determination of the investigator or Sponsor
- Any investigational treatment other than gantenerumab during or since completion of the OLEs of Studies WN25203 or WN28745
- Pregnancy
- Evidence of disseminated leptomeningeal hemosiderosis (i.e., more than three focal leptomeningeal hemosiderosis)
- Evidence of intracerebral macrohemorrhage

4.1.3 Eligibility in Part 2

- *All participants who have completed Week 104 visit in Part 1 of the study and have not been discontinued from Part 1 of the study can continue to participate in Part 2 of the study*
- *The criteria mentioned in Sections 4.1.1 and 4.1.2 will also be applicable to Part 2 of the study*

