5.3.5.1 Amyloid-related Imaging Abnormality Findings

Not every ARIA finding in MRI qualifies as an adverse event. An ARIA finding must be reported as an adverse event if it meets any of the following criteria:

- ARIA-E which is symptomatic (i.e., accompanied by CNS symptoms), and/or
- ARIA that results in a change in study treatment (e.g., dosage modification, treatment interruption, or treatment discontinuation), and/or
- Is otherwise clinically significant in the investigator's judgment

Any accompanying symptoms should also be captured as separate adverse events.

It is the investigator's responsibility to review all ARIA findings.

Observations of the same clinically significant ARIA finding should only be recorded once on the adverse event eCRF (see Section 5.3.5.5 for details on recording persistent adverse events).

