Appendix 2 Management Rules for Amyloid-Related Imaging Abnormalities

Event	Characteristics	Action to be Taken
ARIA-E	Asymptomatic ARIA-E ≥ 1 and < 4 BGTS	
Participants who had MRI on target dose:
 
 • Continue study drug at the same dose level and perform MRI scans at 4-week intervals until ARIA-E resolves, then resume the standard MRI schedule (Appendix 1) 
Participants who had MRI prior to up-titration to target dose:
 
 • Continue study drug and do not up-titrate. Repeat MRI scan 4 weeks later • As long as BGTS is < 4 and ≥ 1, continue study drug at the same dose level and continue MRI monitoring at 4-week interval • Once ARIA-E resolves, complete up-titration to target dose and resume the standard MRI schedule (Appendix 1)
	Symptomatic ARIA-E (of any size) or asymptomatic ARIA-E and BGTS ≥ 4	
Participants who had MRI on target dose:
 
 • Temporarily interrupt study drug and perform MRI scans at 4-week intervals until symptoms and ARIA-E resolve • When symptoms and ARIA-E resolve, reintroduce study drug at target dose and resume the standard MRI schedule (Appendix 1) 
Participants who had MRI prior to up-titration to target dose:
 
 • Temporarily interrupt study drug and perform MRI scans at 4-week intervals until symptoms and ARIA-E resolve • When symptoms and ARIA-E resolve, reintroduce study drug at the dose level given at the time the event was detected • After one dose at the dose level given at the time the event was detected, but before the next scheduled dose, perform a subsequent MRI scan • If no new ARIA-E is detected, then complete up-titration to target dose and resume the standard MRI schedule (Appendix 1)
	Any recurrence of ARIA-E	
 • Treat as above (based on symptoms and BGTS)
ARIA-H	Any disseminated LH (more than 3 focal LH)	
Permanently discontinue study drug
 
Note: In the absence of disseminated LH, study drug can be continued, including up-titration to target dose

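### Does Section 6.5 need to say how ARIA already present on the Day 1 MRI enters the ARIA incidence?

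*Combined protocol and SAP*

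**What the plan says.** Section 6.5 defines the safety population as everyone who received at least one dose and lists the outcomes to be summarised descriptively, among them "Incidence, nature, severity, and timing of MRI safety findings: ARIA-E and ARIA-H". Vital signs, blood tests, ECGs and C-SSRS are tied to the baseline of this study; the ARIA bullet carries no such anchor. The section closes: "Statistical methods, endpoint definitions and analyses of the safety endpoints will be described in the Statistical Analysis Plan".

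Section 1.2.2 reports the parent extensions in terms of new findings. For Study WN25203, "47 participants (30.5%) had new ARIA-E and 51 participants (33.1%) had new ARIA-H", out of 154 dosed participants, all with a post-baseline MRI. For Study WN28745, "71 participants (32.4%) had new ARIA-E and 75 participants (34.24%) had new ARIA-H", out of the 219 of 225 dosed who had a post-baseline MRI.

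Some ARIA can be present at entry. Besides macrohemorrhage, the only ARIA-H exclusion in Section 4.1.2 is "Evidence of disseminated leptomeningeal hemosiderosis (i.e., more than three focal leptomeningeal hemosiderosis". Sections 3.1.1 and 5.1.2 provide for ARIA-E still ongoing at Day 1. Appendix 2 has a row for "Any recurrence of ARIA-E", and on ARIA-H it notes: "In the absence of disseminated LH, study drug can be continued, including up-titration to target dose".

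Section 5.3.5.1 warns: "Not every ARIA finding in MRI qualifies as an adverse event". It requires adverse event reporting for symptomatic ARIA-E, for ARIA that changes study treatment, and for ARIA the investigator judges clinically significant.

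**The concern.** In a rollover study, some participants may already have ARIA-H on the Day 1 scan. For them, new ARIA-H could mean an additional lesion, or it could mean that they cannot have the event at all. On the second reading, keeping them in an all-dosed denominator dilutes the percentage. If additional lesions are not counted, worsening is missing from the headline figure. ARIA-E raises a similar question: is a recurrence in someone with ARIA-E ongoing at Day 1 an incident finding?

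The adverse event rules do not fully close the gap. Appendix 2 changes treatment for ARIA-H only when leptomeningeal hemosiderosis is disseminated. Much carried-over ARIA-H may therefore never have been an adverse event, and the medical-history rule in Section 5.3.5.10 would not reach it.

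ARIA is an identified risk and safety is the main objective. What is at stake is whether a reader can interpret the ARIA percentage and set it beside the parent-extension figures.

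**Working it through.** **1. The parent figures and their denominator (Section 1.2.2).**

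- WN25203: ARIA-E 47/154 = 30.5%; ARIA-H 51/154 = 33.1%. Both match.
- WN28745: ARIA-E 71/219 = 32.4%, which matches; ARIA-H 75/219 = 34.25%, printed as 34.24%, a rounding difference. Over the 225 dosed the results would be 31.6% and 33.3%, so the denominator was participants with a post-baseline MRI.
- Pooled new ARIA-H: (51 + 75)/(154 + 219) = 126/373 = 33.8%.

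These extensions themselves followed double-blind phases in which 11.8% to 22.9% of participants had ARIA-H, depending on study and arm. They still reported new findings over everyone with a later MRI; Section 1.2.2 describes no restriction to finding-free participants. The sponsor has already met the carry-over question, and the denominator it used can be seen.

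**2. How far the denominator could move the result.** The documents do not give the number with ARIA-H at Day 1. Assume the 116 Part 1 participants (Section 6.1) had the pooled rate: 0.338 × 116 ≈ 39. Assume further that 25%, 50% or 100% of these are still visible at Day 1, and that 10 participants free of ARIA-H at Day 1 develop it during the study.

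| Still visible at Day 1 | Carried over | At risk | 10 / 116 | 10 / at risk | Ratio |
|---|---|---|---|---|---|
| 25% | 10 | 106 | 8.6% | 9.4% | 1.09 |
| 50% | 20 | 96 | 8.6% | 10.4% | 1.21 |
| 100% | 39 | 77 | 8.6% | 13.0% | 1.51 |

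The exact (Clopper-Pearson) 95% interval for 10/116 is 4.2% to 15.3%, which contains every value in the table.

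Counting any ARIA-H seen on a later scan, old or new, would give (10 + 10)/116 = 17.2%, (20 + 10)/116 = 25.9% or (39 + 10)/116 = 42.2%. That reading would break with the parent convention and is unlikely.

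**3. What the recording rules already catch.**

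- *Recurrence.* Section 5.3.5.5 records each recurrence of an adverse event as a separate event. Under Appendix 2, ARIA-E that is symptomatic or has a Barkhof grand total score of 4 or more on MRI interrupts dosing, so under Section 5.3.5.1 it is an adverse event. What escapes is an asymptomatic recurrence with a score below 4 that changes no treatment and is not judged clinically significant.
- *Worsening ARIA-H.* Progression to disseminated leptomeningeal hemosiderosis leads to permanent discontinuation (Section 4.6.1, Appendix 2) and is therefore an adverse event. Other clinically significant worsening is reportable under Sections 5.3.5.1 and 5.3.5.10. What escapes is additional lesions below those thresholds.
- *Reporting and oversight.* Section 6.5 also commits to nature, severity and timing of the MRI findings. Under Section 5.1.1.1 the Internal Monitoring Committee reviews safety findings at individual and aggregate level.

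Two narrow cases remain: sub-threshold additional ARIA-H lesions, and low-score asymptomatic ARIA-E recurrence. Both concern how one descriptive percentage is counted.

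**The case for a change.** The strongest case for a change is that reuse of the parent convention is an inference. Nothing in Section 6.5 imports it, and the population named there is all dosed participants, whereas the WN28745 percentages used those with a post-baseline MRI. Nor does Section 1.2.2 say whether a further lesion in someone with earlier ARIA-H counted as new. A sentence in the SAP and one or two table rows would settle this from central MRI reads already collected, at almost no cost.

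Those statements about the text are correct, and the count of additional lesions is not defined in the documents at hand. But Section 6.5 assigns exactly this kind of definition to the SAP. A short protocol list that points to the SAP does not show that the rule is missing from the plan, and its bullets on adverse events, injection-site reactions and anti-drug antibodies are written at the same level of detail. Extra rows for worsening and recurrence would be a useful display; they would not correct a stated rule that gives a wrong answer.

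**Conclusion.** No change is needed. This is a definition the protocol expressly leaves to the SAP, with a visible sponsor precedent that analysts can sensibly follow. No rule in the text produces a wrong result. The events that matter most clinically are captured as adverse events whichever way the MRI percentage is counted.

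Under the assumptions above, the choice between an all-dosed and an at-risk denominator moves ARIA-H incidence by 0.8 to 1.8 percentage points if a quarter or a half of the assumed cases persist to Day 1 (9.4% − 8.6% and 10.4% − 8.6%), and by 4.4 points if all do (13.0% − 8.6%). These sizes are illustrative. Day 1 prevalence, persistence and the 10 events are not in the documents, and the parent rate is an imperfect proxy: it omits ARIA-H from before the extensions and includes participants who did not complete them. The study is single-arm and descriptive, with no hypothesis test or threshold attached to this percentage, so none of its conclusions turns on the choice.
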